#### **Time-weighted Summed Pain Intensity Difference (SPID) at 30-minute intervals:**

Time-weighted SPID measurements will be calculated at approximate 30-minute intervals until discharge from the ED (up to 120 minutes) or rescue narcotic administration, will be determined when feasible. Essentially, the SPID represents serial assessments of pain intensity over time, weighted by time differences. SPID will be calculated using values from a 101-point continuous pain intensity scale (0 = no pain to 100= worst pain imaginable). The Pain Intensity Difference (PID) (e.g., raw differences in pain intensity) is calculated by subtracting the pain intensity at each time point from the pain intensity at time 0. The SPID is then calculated by multiplying the PID score at each post dose time point by the duration (in hours) since the preceding time point and then summing the values over the relevant time period. If patients did not complete the full 120 minutes, the last pain observation was carried forward.

#### Number of rescue doses of narcotic at 30 minutes and until ED discharge (up to 120

**minutes):** The number of doses of standard care pain treatment given within 30 minutes following randomly assigned intervention and total until ED discharge (up to 120 minutes), when feasible.

#### Time to reduction of VNRS pain score of 10 points (up to 120 minutes)

The time in minutes will be determined for the VNRS pain score (0-100) to be reduced by 10 points following randomized assignment administration for patients, when feasible.

Cognitive function at 30 minutes using Six Item Screener (SIS): The SIS will be used to detect cognitive impairment (e.g., sleepiness, confusion, memory impairment and reaction time)

at 30 minutes. Using a cutoff of  $\leq$  4 (out of 6) to reflect cognitive impairment has been proposed for ED use and has been used in prior studies of treatment of acute pain with sufentanil in the ED.

Healthcare Professional Global Assessment (HPGA) of the Method of Pain Control at 30 minutes: The HPGA of the method of pain control will also be reported by the healthcare professional (primarily nurses) at the 30-minute time period as the PGA above.

Acceptability to health care providers survey: An acceptability to health care providers score will be requested of health care providers in the ED including ED nurse, ED trauma team member and/or trauma surgery team member at 30 minutes or when feasible. The score (-2 to +2; 5-point scale) ratings will be from; very dissatisfied, dissatisfied, neither satisfied nor dissatisfied, satisfied, very satisfied, and will document providers assessment regarding the individual patient's pain management process, ease and acceptability relative to past experiences, when feasible.

Predefined Subgroups: Predefined subset analyses will be performed on: sex (male/female), Injury Severity Score (ISS  $< or \ge 16$ ), age ( $< or \ge 50$ ), blunt versus penetrating injury, history of pre-injury opioid use (Y/N), air versus ground prehospital transport, transport origin (scene versus outside ED).

## V. Screening and Enrollment

Subjects will be identified prospectively in the ED by research personnel that are trained and familiar with the inclusion and exclusion criteria. Those patients who meet all inclusion and no exclusion criteria will be approached for informed consent, and once obtained, randomized to DSUVIA or standard care based upon the predetermined randomization assignment. Subjects will be paid \$25.00 in a Vincent Pay card upon completion of the study.

## VI. Statistical Analysis Plan

Random Assignment: Participants will be randomly assigned in a 1:1 ratio to either DSUVIA or standard of care, stratified by site. Within each stratum, random assignment will be blocked, with random block size of two and four.

Analyses: All analyses will be carried out based on the intention-to-treat principle. Of those randomly assigned, the analyses will begin by describing the overall characteristics of the study population at the time of random assignment. Baseline characteristics will be described overall using summary statistics (e.g., means, standard deviation, percentages) and graphical techniques (e.g., histograms, box plots). Baseline characteristics between the two groups will be compared using t-tests or Wilcoxon tests for continuous variables and a chi-square tests for discrete variables.

The analyses for each aim are presented below.

AIM #1: To determine if, among injured patients with moderate to severe pain, treatment with DSUVIA compared to standard care pain treatment in the ED reduces the Verbally Administered Numeric Rating Scale (VNRS) for clinical pain measurement (0-100) at 30 minutes.

A t-test will be used to compare the mean VNRS scores between the two treatment groups. A multivariable regression model will be used to compare the means after adjusting for stratification

variables (i.e., site) and baseline characteristics not balanced through random assignment. All assumptions of the analyses will be tested (e.g., normality of residuals). If any assumptions are violated, transformations of the data will be investigated and the transformed data will be analyzed and evaluated. If an adequate transformation cannot be identified, nonparametric methods will be used.

AIM #2: To determine if, among injured patients with moderate to severe pain, treatment with DSUVIA compared to standard care pain treatment in the ED reduces adverse effects and events related to pain medication(s) including nausea/vomiting, headache, dizziness, hypoxia, hypotension, and need for advanced airway.

The adverse events will be analyzed in composite (any of them) and individually. For each, a chi-square test will be to compare the proportion of events between the two treatment groups. A multivariable logistic regression model will be used to compare the proportions after adjusting for stratification variables (i.e., site) and baseline characteristics not balanced through random assignment

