The NAEMSP guidelines focus on intravenous (IV) fentanyl and morphine because of wide availability among American EMS services. Use of IV opioids is limited by the need to obtain IV access, which can be time consuming, is associated with a significant failure rate, and may lead to increased exposure in a tactical environment. The US military uses oral transmucosal fentanyl citrate (OTFC) which can be administered without IV access, but has slow absorption. Furthermore, safety data on OTFC, outside of long-term analgesia for cancer patients, is not well described. Given these significant limitations, an alternative to IV opioid analgesics in necessary. The ideal agent has robust stability, easy delivery, rapid onset, minimizes altered mental status and has a wide therapeutic index. In addition, the ideal agent would have a longer duration of action and an improved side effect profile as compared to the current standard care.

Sufentanil is a potent opioid analgesic derived from fentanyl with no active metabolites, rapid onset, and a therapeutic index superior to morphine and fentanyl. Sufentanil is highly lipophilic and rapidly achieves equilibrium in the brain; the time to analgesia is similar to IV morphine. When administered sublingually, sufentanil is 53% of the IV bioavailability within one minute and provides analgesia within 15 minutes. Sufentanil has a low incidence of side effects, with nausea, headache, dizziness, and vomiting being the most common. As with any opioid, respiratory depression and hypoxia can occur but was observed to be <1%. Similar studies found no clinically significant changes in vital signs after the administration of sublingual sufentanil in post-operative patients. Sufentanil was effective in a cohort of patients with painful injuries presenting to the ED with pain reduction seen in less than 15 minutes and persisting for 2 hours.

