#### Secondary Outcome Definitions:

**Hypoxia, hypotension or need for advanced airway:** The principal safety outcome for the trial will be the incidence of serious adverse events following the first dose of analgesic following randomization including hypoxia (SpO2 < 90%), hypotension (SBP < 90 mmHg) or the need for advanced airway management (placement of an endotracheal tube, supraglottic airway or bag mask ventilation) until ED discharge (up to 120 minutes), when feasible.

Composite outcome of nausea, vomiting, headache, and/or dizziness requiring treatment: The incidence of nausea, vomiting, headache, and/or dizziness requiring treatment will be recorded for initial 30 minutes, when feasible.

Verbally administered Numeric Rating Scale (VNRS) pain measurements (0-100) at 30- minute intervals: VNRS for clinical pain (0-100) measurements at approximate 30-minute intervals until discharge from the ED (up to 120 minutes) or rescue narcotic administration, will be obtained when feasible.

**Patient Global Assessment (PGA) of Pain Control at 30-minute intervals:** The PGA of the method of pain control at approximate 30-minute intervals until discharge from the ED (up to 120 minutes) or rescue narcotic administration, will be obtained when feasible. The research team will read the following statement aloud to the subject and the response will be recorded: "Overall, would you rate this method of pain control during the last 30 minutes/hours as being poor (1), fair (2), good (3), or excellent (4)?"

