Randomization of Ineligible Subjects: It is anticipated that there will be a small proportion of patients enrolled who receive DSUVIA or standard care that in retrospect will not have met the entry criteria and are thus ineligible. In this circumstance, patients will be analyzed according to the group to which they were randomized. Subgroup analyses based on eligibility criteria will be performed if the number of patients so affected is large. However, based on the relatively limited inclusion and exclusion criteria it is anticipated that the frequency of this event will be low.

Non-adherence: In some circumstances, patients may receive standard care instead of the DSUVIA intervention when randomized to DSUVIA. Non-adherence is most likely to occur in the case of the patient who requires intervention and despite DSUVIA being available, is unable to be provided. In the event of inappropriate handling or unsuccessful administration of the DSUVIA, a second dose of DSUVIA may not be administered. Once a physician has assessed the subject, if appropriate, the subject may receive a dose of standard care pain medication and continue in the DEEP study. Fortunately, this event is relatively rare. In keeping with the intention-to-treat analytic design, these patients will be analyzed with the group to which they were randomized.

Interim Analyses: Throughout the course of the study, the DSMB will review recruitment, retention, adherence to assigned intervention, data completeness, protocol deviations, and adverse events. Safety data will be examined on an ad hoc basis in the event that unexpected safety concerns arise from study data or from external research or literature.

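### Aim 2 adverse events are compared only by randomized arm, so no analysis describes safety by the drug patients actually received

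*Combined protocol and SAP*

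**What the plan says.** Section VI (Analyses) sets one rule for the whole trial: "All analyses will be carried out based on the intention-to-treat principle". Aim 2 follows under that rule: for the composite and for each adverse event, "a chi-square test will be to compare the proportion of events between the two treatment groups", with an adjusted logistic model beside it.

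Section VI (Non-adherence) says that "patients may receive standard care instead of the DSUVIA intervention when randomized to DSUVIA". After mishandled or unsuccessful administration of DSUVIA, "the subject may receive a dose of standard care pain medication and continue in the DEEP study". It then confirms that "these patients will be analyzed with the group to which they were randomized". On frequency it says only: "Fortunately, this event is relatively rare". No rate is given, and no switch from standard care to DSUVIA is described.

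Section IV (Secondary Outcome Definitions) starts the safety window at any analgesic, not at DSUVIA: "The principal safety outcome for the trial will be the incidence of serious adverse events following the first dose of analgesic following randomization". The window runs to ED discharge, at most 120 minutes.

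The documents name no safety population, no as-received analysis and no sensitivity analysis by drug received.

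**The concern.** The study objectives in the Synopsis include the safety of DSUVIA, and Section II closes by calling for its efficacy and safety to be determined. That is partly a question about exposure: what happens to patients who take the drug. A comparison by assignment answers a different and legitimate question: what happens when DSUVIA is the intended treatment. The plan answers only the second.

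A patient assigned to DSUVIA who receives only standard care enters the DSUVIA safety figures in either case. With an event, that patient adds to the DSUVIA numerator. Without one, the patient adds an unexposed person to the denominator. Either way the DSUVIA-arm rate is pulled towards the standard-care rate. At stake are the reported DSUVIA event rates and the safety results by treatment group that Section VI (Interim Analyses) lists among the DSMB's inputs to a stopping recommendation.

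**Working it through.** **The plan's own figure.** There is none to reproduce here. The plan states no event rate, power or sample size for Aim 2; its only power figure (80% with 75 per group) belongs to the pain score.

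**Inputs.** From the documents: 75 patients per arm, 1:1 allocation, one-way switching. Assumed: the share p of the DSUVIA arm that receives only standard care (1% to 20%) and the event risks by drug.

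**Dilution.** Let r_D and r_S be the risks on DSUVIA and on standard care, and let switched patients carry r_S.

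- DSUVIA-arm rate = (1 − p)·r_D + p·r_S
- Difference between arms = (1 − p)·r_D + p·r_S − r_S = (1 − p)·(r_D − r_S)

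The difference shrinks by the fraction p, whichever drug is safer: 1% at p = 1%, 5% at p = 5%.

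**Effect on power.** Two-sided 0.05; 75 v 75 by arm, 75(1 − p) v 75(1 + p) by drug received; all risks assumed. Each cell shows power by arm / by drug received.

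| DSUVIA v standard care | p = 1% | p = 5% | p = 10% | p = 20% |
|---|---|---|---|---|
| 10% v 30% | 86.4 / 87.2 | 82.9 / 87.0 | 77.8 / 86.6 | 66.0 / 85.2 |
| 5% v 20% | 78.9 / 79.9 | 74.6 / 79.4 | 68.7 / 78.7 | 56.4 / 76.5 |
| 5% v 1% (DSUVIA worse) | 29.5 / 30.2 | 28.2 / 31.2 | 26.5 / 32.4 | 23.2 / 34.5 |

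At p = 1–5% the cost is about 1 to 5 points; at p = 20% it is about 11 to 20 points. In the harm scenario power is low under either grouping.

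**One reclassified case.** Section II puts respiratory depression and hypoxia with sufentanil below 1%, so fewer than 75 × 0.01 = 0.75 events are expected in the arm. Suppose the only hypoxia event in the DSUVIA arm is in its one switched patient.

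- By arm: 1/75 = 1.3% (exact 95% upper limit 7.2%)
- By drug received: 0/74 (upper limit 1 − 0.025^(1/74) = 4.9%)

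The expected number of such cases is 75 × p × r_S. At r_S = 1% this is 75 × 0.01 × 0.01 = 0.0075 for p = 1% and 75 × 0.05 × 0.01 = 0.0375 for p = 5%. At r_S = 5% it is 0.0375 and 0.1875. The example is possible but unlikely.

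**What the as-received grouping can get wrong.** Suppose both drugs carry the same risk, but the 5% of patients who would be switched have a risk of 20% and the rest 5% (all assumed).

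- By arm: both arms 0.95 × 5% + 0.05 × 20% = 5.75%, difference 0
- By drug received: DSUVIA 5%; standard care (75 × 5.75% + 3.75 × 20%) / 78.75 = 5.0625 / 78.75 = 6.4%

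The as-received table would then favour DSUVIA by about 1.4 points with no true difference.

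**The case against.** The strongest reply is that intention to treat is valid and consistent for comparing two open-label strategies, and that the plan itself calls non-receipt rare. Both parts stand. A reader might infer that applying intention to treat to safety is an error, or that a real harm of DSUVIA would be hidden. The documents support neither: the arm comparison is a proper randomized estimate, and at a rare rate the shrinkage is a few per cent.

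Direction is also not all one way. Aim 2 asks whether DSUVIA reduces adverse events, and for that claim shrinkage towards no difference is conservative. It works against the reader only when the question is whether DSUVIA does harm.

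A reader might further infer that the misplaced events would follow an IV opioid. The background describes standard care in those terms, but neither the Standard Care Arm text nor the Non-adherence paragraph fixes a drug or route.

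It can be said, too, that the matter is partly covered: sites judge each event's relationship to the study intervention (Section X), and the DSMB reviews adherence and adverse events. That gives some visibility, but it does not change the Aim 2 comparison or produce rates by drug received.

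Finally, the (1 − p) formula assumes that switched patients carry average standard-care risk. The Non-adherence paragraph expects non-receipt chiefly in patients who need intervention, so their risk may be higher. This stands. It is why an as-received analysis cannot replace the randomized one.

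**Conclusion.** The gap is real and minor. Aim 2 is analysed only by randomized arm, patients who never took DSUVIA can be counted in the DSUVIA safety figures, and no analysis by drug received is planned. The dilution is (1 − p), which is 1–5% relative at p = 1–5%. That rests on an assumed p, one-way switching as the plan describes it, and average standard-care risk in switched patients. If non-receipt proved common (20%), the difference would shrink by a fifth. With few events, one reclassified case can change the reported DSUVIA rate, but at low p and low event risk it is unlikely to arise. This calls for a supportive analysis, not for a change of the primary safety comparison.

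**What to change.** Keep intention to treat for all aims, including the Aim 2 comparison. In Section VI (Analyses, Aim 2) add one prespecified supportive analysis by treatment received:

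- DSUVIA: any DSUVIA exposure, including partial or failed delivery.
- Standard care: no DSUVIA exposure.

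Report it beside the randomized result, with the number of patients who change group, and give the same table to the DSMB. Confirm that the case report form captures the drug actually given in the DSUVIA arm. Section III states such recording explicitly only for the standard care arm and for treatment before randomization.

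The cost is a short SAP paragraph, one extra set of tables and possibly one form field. The sample size, primary analysis and treatment rules do not change. The downsides should be stated with the table: the groups are not fully randomized, switched patients may differ in risk, and events after rescue narcotic in patients who did take DSUVIA remain under DSUVIA. Fixing the definition now avoids reclassifying patients after their events are known.

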#### Inclusion Criteria

- 1. Trauma activation (Level I, II or III)
- 2. Age 18-70 years inclusive.
- 3. Need for pain treatment based upon an NRS (0-100) clinical pain measurement  $\geq 50$
- 4. Estimated time in Emergency Department > 30 minutes following informed consent

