# AIM #4: To determine if, among injured patients with moderate to severe pain, treatment with DSUVIA compared to standard care pain treatment in the ED improves Healthcare Professional Global Assessment (HPGA) of the Method of Pain Control and health care provider survey scores.

Scores to the HPGA will be based on a four-point scale. A 2x4 chi-square test will be used to compare the distribution of scores across the two treatment groups. An ordinal polytomous logistic regression model will be used to compare the distribution of proportions after controlling for stratification (sites) and baseline characteristics not balanced through random assignment. The same analysis will be repeated on the health care provider survey scores, with the modification to account for a five-level outcome.

**Sample Size**: The sample size calculations are based on the analyses of the primary aim (Aim 1) of the study. To detect a minimum effect size of 0.45, a sample size of 150 subject is needed (75 per group), assuming a type I error of 0.05, a two-sided alternative hypothesis, and 80% power. Thus, assuming a standard deviation of 21 (Karcioglu, 2003), a difference of 7.1 can be detected between the mean VNRS scores.

**Missing data**: Every attempt will be made to minimize the amount of missing data. Give the short timewindow to collect data, missing data should be minimal. However, in the event that there is missing data for the outcomes, the pattern of missingness will be evaluated. Assuming that the data will be missing at random, multiple imputation techniques will be used to impute data and carry out the proposed analyses.

**Subgroup**: Analyses will be carried out for pre-defined subgroups, specifically: sex (male/female), Injury Severity Score (ISS < or  $\ge 16$ ), age (< or  $\ge 50$ ), blunt versus penetrating injury, history of prior opioid use (Y/N), air versus ground prehospital transport, transport origin (scene versus outside ED). For all subgroup analyses, regression models will be used to assess if there is a differential treatment effect by subgroup. Regression models will include main effects for treatment and the indicator of the subgroup, as well as the two-way interaction between treatment and the subgroup indicator. A statistically significant interaction will indicate a differential treatment effect.

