The DSMB will review the primary and secondary outcomes bi-annually. Prior to initiation of the trial, the final monitoring plan will be developed to serve as the guide to the DSMB's decision-making process concerning early stopping of the trial. The interim analysis will consist of two components, efficacy evaluation and futility evaluation. The purpose of the efficacy evaluation is to detect early sign of treatment effect early in the study. The purpose of the futility analysis is to assess if the study is unlikely to achieve a statistically significant effect. In making the decision to recommend termination of the study, the DSMB shall be guided by several types of information: (i) a formal stopping rule based on the primary analysis (comparison of treatment groups on the primary outcome), (ii) information on safety outcomes by treatment group, (iii) consistency between results for primary and secondary outcomes, (iv) consistency of treatment effects across subgroups, and (v) conditional power.

We have designed this trial with one-interim analyses before the final analysis. The number of interim analyses will be finalized in discussion with the DSMB prior to the initiation of the study. The interim analysis plan is based on the Lan and Demets approach utilizing an O'Brien-Fleming spending function to

determine alpha spending and test boundaries. A formal interim analysis of efficacy will be performed when 50% of the randomly assigned participants have completed the assessment of the primary outcome. We will use a t-test to test for difference. The level of significance will maintain an overall p-value of 0.05 according to O'Brien-Fleming stopping boundaries leaving a p value of 0.003 and 0.049 for the interim and final analyses, respectively. This translates to a two-sided z-value for the interim and final analyses of +/-2.96 and +/-1.97, respectively.

In addition, the futility of the study will be evaluated at the time an interim efficacy test is conducted. Specifically, the conditional power will be calculated. If the condition power is less than value prespecified by the DSMB (e.g., <20%), we can conclude that it would be futile to continue with the investigation.

Surveillance for Outcomes and Data Elements: Data will be collected prospectively as patient care progresses. This will include a review of the prehospital patient care report(s), ED and electronic/ paper hospital records.

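### Aim 1 appears to rest on an unadjusted t-test and never names baseline VNRS as a covariate; always adjusting for it would be a nearly free, probably modest, gain in precision

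*Combined protocol and SAP*

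**What the plan says.** Section VI (Analyses, AIM #1) opens with "A t-test will be used to compare the mean VNRS scores between the two treatment groups". A multivariable regression follows, adjusting for stratification "variables (i.e., site) and baseline characteristics not balanced through random assignment". No threshold defines imbalance, although the same section says baseline characteristics will be compared with t-tests or Wilcoxon tests. If model assumptions fail, transformations are tried, and then "If an adequate transformation cannot be identified, nonparametric methods will be used".

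The plan does not say whether the t-test or the regression decides Aim 1. Two other places point to the t-test. Section VI (Interim Analyses) bases the formal stopping rule on the primary analysis and says "We will use a t-test to test for difference". The Sample Size paragraph involves no covariate: "To detect a minimum effect size of 0.45, a sample size of 150 subject is needed (75 per group"). The interim text is the stronger evidence, since a covariate-free calculation would also fit an adjusted analysis.

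Random Assignment says "Participants will be randomly assigned in a 1:1 ratio to either DSUVIA or standard of care, stratified by site". Among the Section III entry criteria is "Need for pain treatment based upon an NRS (0-100) clinical pain measurement" of at least 50, and Section V places consent and randomization after eligibility is established. A pain score therefore exists before randomization. None of the models for Aims 1 to 4 names it as a covariate.

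**The concern.** A baseline score that predicts the outcome reduces residual variance whether or not the arms happen to look balanced on it. The t-test uses neither that score nor site, the stratification factor. The supporting regression always has site but admits baseline VNRS only after an observed imbalance. That criterion selects on chance imbalance rather than prognostic value, and it has no stated threshold.

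Two things are at stake. One is power, in a design that falls slightly short of 80% at its own effect size. The other is specification: the covariate set and the deciding Aim 1 analysis are not fixed before the data are seen, in an open-label trial. Neither makes the planned t-test invalid.

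**Working it through.** **Inputs from the plan (Section VI).** 75 per arm; two-sided alpha 0.05; standardized effect 0.45; SD 21; stated detectable difference 7.1; final-look significance level 0.049. **Assumed.** r, the within-arm correlation of baseline with 30-minute VNRS, which the documents do not give.

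**1. The plan's own figure.** The noncentrality is 9.45 / (21 × √(2/75)) = 9.45 / 3.43 = 2.76 on 148 df. Power is 78.2% by noncentral t (78.7% by normal approximation), close to the stated 80%. Exactly 80% needs 79 per arm (78 by normal approximation). At alpha 0.049, power is 77.9%.

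The plan also says "a difference of 7.1 can be detected between the mean VNRS scores". That does not follow from its own inputs, since 0.45 × 21 = 9.45. Power for 7.1 points is 54%.

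**2. Always adjusting.** Residual SD = 21 × √(1 − r²), with 4 covariate df (baseline VNRS plus up to 3 for site). The lower figure in each power range multiplies the variance by (1 + 1/df) to allow for chance baseline imbalance.

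| r | Residual SD | Power at 9.45 | Power at 7.1 | Difference detectable with 80% power |
|---|---|---|---|---|
| unadjusted | 21.00 | 78.2% | 53.9% | 9.67 |
| 0.1 | 20.89 | 78.3-78.6% | 54.0-54.3% | 9.62 |
| 0.2 | 20.58 | 79.5-79.8% | 55.2-55.5% | 9.48 |
| 0.3 | 20.03 | 81.6-81.8% | 57.5-57.8% | 9.23 |
| 0.4 | 19.25 | 84.5-84.8% | 60.9-61.2% | 8.86 |
| 0.5 | 18.19 | 88.3-88.5% | 65.8-66.1% | 8.38 |

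At r = 0, power at 9.45 is 77.9-78.1%, so the most that can be lost is about 0.3 points.

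**3. Which r is plausible.** Entry at 50 or above narrows the baseline range and so weakens the correlation. If v is the ratio of truncated to unselected baseline variance, the correlation among enrolled patients is r√v / √(1 − r² + r²v). Take a normal baseline truncated to 50-100, with assumed unselected mean and SD of 60 and 25, 65 and 21, 70 and 20, or 75 and 15:

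| Unselected r | r among enrolled patients |
|---|---|
| 0.2 | 0.11-0.16 |
| 0.3 | 0.16-0.24 |
| 0.4 | 0.22-0.33 |
| 0.5 | 0.29-0.42 |
| 0.6 | 0.37-0.51 |

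**4. Adjusting only after an imbalance.** The standardized baseline difference has standard error √(2/75) = 0.163. Under three assumed readings of imbalance, baseline VNRS would enter in 5% of trials (p < 0.05), 22% (standardized difference above 0.2) or 54% (above 0.1). Simulated power at 9.45 points (25,000 trials per r, 3 sites, no site effect):

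| r | t-test | p < 0.05 rule | > 0.2 rule | > 0.1 rule | Always adjusted |
|---|---|---|---|---|---|
| 0.1 | 78.3% | 78.3% | 78.3% | 78.4% | 78.5% |
| 0.2 | 78.3% | 78.3% | 78.6% | 79.0% | 79.6% |
| 0.3 | 78.0% | 78.3% | 79.0% | 80.1% | 81.4% |
| 0.4 | 78.6% | 79.1% | 80.7% | 82.5% | 84.8% |
| 0.5 | 78.5% | 79.5% | 82.1% | 85.3% | 88.5% |

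**5. Type I error.** With no true effect, always adjusting gave 5.1% at r = 0.3 and 4.9% at r = 0.5 (40,000 trials each). With scores rounded to tens and clipped to 0-100 (four scenarios, 20,000 null trials each), it gave 4.9-5.2%, so the regression holds up on coarse, bounded data.

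**6. When the baseline score is taken.** Suppose the baseline SD is 13 and knowledge of assignment shifts the reported baseline by 2-4 points in one arm. The bias is the shift times r × 21/13: from 2 × 0.3 × 21/13 = 1.0 to 4 × 0.5 × 21/13 = 3.2 points. Type I error is then 6-19%. The covariate must predate randomization.

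**The case against.** The strongest reply is that nothing here is an error. A t-test is valid in a 1:1 trial stratified by site, and an adjusted regression that could include baseline VNRS is already planned. The benefit depends on a correlation the documents do not supply. About r = 0.5 among enrolled patients arises only in the most favorable assumed case (unselected r = 0.6, mean 75, SD 15); an unselected 0.4 gives roughly 2 to 4 points of power. Section III also allows pain treatment before randomization, which could change the correlation further. All of this stands, and it limits the size of the claim.

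The plan runs the t-test and the regression side by side and does not switch between them, and the imbalance thresholds above are assumed. That also stands. Those columns matter only if the regression decides, and they show that its present covariate rule would then recover only part of the gain.

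Imbalance-triggered adjustment does not inflate type I error. Switching from the t-test to the adjusted model at a standardized difference above 0.1 or 0.2 gave about 4.5-4.6% at r = 0.3 and 3.8-3.9% at r = 0.5. The cost of that rule is power, not false positives.

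Finally, the data-element list in Section VI does not name a baseline VNRS. The score is nevertheless required for eligibility, so what is missing is a recorded, timed value rather than a new measurement. None of these points shows a material downside to adjusting.

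**Conclusion.** The point holds as a free improvement, not a validity error. The apparent deciding test for Aim 1 is unadjusted, and whether baseline VNRS enters any model depends on an unstated rule.

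At 9.45 points, always adjusting raises power from 78% to between 78-79% (r = 0.1) and about 88% (r = 0.5). With entry restricted to scores of 50 or more, the low to middle part of that range is more likely. An r of 0.2 to 0.3 would bring the design to about its stated 80%. The downside at r = 0 is about 0.3 points.

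These figures rest on assumed correlations, SD 21, no missing outcomes and alpha 0.05; the final-look level of 0.049 takes about 0.3 points off the unadjusted figure. No gain is claimed from site or at the interim look. Adjustment does not repair the conflict between 7.1 and 9.45: at 7.1 points, power stays at 54-66% over r = 0.1 to 0.5.

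**What to change.** In Section VI, name one primary Aim 1 analysis for both the interim and final looks: a linear regression of 30-minute VNRS on treatment, site and baseline VNRS. Apply the interim and final boundaries to the treatment coefficient.

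- Define baseline VNRS as the last score recorded before randomization. The time-0 score in the SPID definition (Section IV) is not tied to randomization, so use it only if it was taken beforehand.
- Remove imbalance-triggered covariates from the Aim 1 model.
- State that this model stays primary whatever the residual checks show. Keep the t-test, any transformed analysis and a rank test as sensitivity analyses.
- State how a missing or untimed baseline score is handled, with the same rule in both arms.

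**Cost.** SAP wording for Aim 1, its assumption-failure fallback and the interim test; a time stamp on the eligibility score; and 2 to 4 of 148 degrees of freedom (1 for baseline VNRS, 1 to 3 for 2 to 4 sites). No added patients, visits or procedures.
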